6.8. Study Vaccination Pausing Rules

The principal investigator (PI) and the study responsible physician/scientist (SRP/SRS) will monitor safety in a blinded manner, including the study vaccination pausing rules. If a study vaccination is considered to raise significant safety concerns (and a specific set of pausing criteria have been met), further vaccination of participants will be paused. The concerned data will be reviewed by the IDMC, after which the IDMC will recommend whether the pause can be lifted or not, or whether other steps are needed.

The IDMC will review blinded data first but has the right to request the randomization codes and review unblinded data if deemed necessary. The IDMC will make recommendations regarding the continuation of the study to the sponsor study team. The sponsor study team will communicate conclusions regarding study continuation to the investigator, the IEC / IRB, and applicable health authorities as appropriate.

After the first IDMC meeting triggered by the occurrence of a given pausing rule, the IDMC will convene thereafter for each additional participant meeting that pausing rule.

The occurrence of any of the following events will lead to a pause in further study vaccination (once the pause is lifted, the decision regarding subsequent vaccination [if applicable] will be

^a Note: Ocular, topical, or inhaled steroids are allowed. Non-immunomodulator treatment is allowed as well as steroids at a physiologic dose.

assessed on a case by-case basis, upon discussion between sponsor and investigator). Laboratory abnormalities noted below refer to cases where the study-site personnel perform laboratory safety testing for investigation of an AE.

1. Death of a participant, considered related to study vaccine or if the causal relationship to the study vaccine cannot be excluded; OR

Note: All cases of death will be sent to IDMC for information. Upon their review, IDMC may then decide whether a study pause is required.
2. One or more participants experience an SAE or a Grade 4 (solicited or unsolicited) AE or a persistent (upon repeat testing) Grade 4 laboratory abnormality that is determined to be related to study vaccine; OR
3. One or more participants experience anaphylaxis or generalized urticaria, clearly not attributable to other causes than vaccination with study vaccine; OR
4. One or more participants experience MIS-C which is assessed as at least possibly related to study vaccine; OR

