5. Three participants from the Dose Selection Cohort (of the same dose level group, within the same age group, and from the same 2 dose vaccination regimen with 1 or 2 active vaccinations, with placebo administered as a second dose for those in the 1-dose regimen) experience a Grade 3 unsolicited AE of the same type (per medical judgement of the sponsor), that is determined to be related to study vaccine; OR
6. Three participants from the Dose Selection Cohort (of the same dose level group, within the same age group, and from the same 2 dose vaccination regimen (56-day interval) with 1 or 2 active vaccinations, with placebo administered as a second dose for those in the 1-dose regimen) experience a persistent (upon repeat testing) Grade 3 laboratory abnormality related to the same laboratory parameter and considered related to study vaccine; OR
7. Three participants from the Dose Selection Cohort (of the same dose level group, within the same age group, and from the same 2 dose vaccination regimen (56-day interval) with 1 or 2 active vaccinations, with placebo administered as a second dose for those in the 1-dose regimen) experience a Grade 3 solicited AE of the same type, determined to be related to study vaccine, and persisting as Grade 3 for longer than 3 consecutive days (ie, the day of occurrence of the AE is counted as Day 1).
8. One or more cases of suspected TTS, possibly related to the vaccine.

For number 2 and number 6: to assess abnormal laboratory values, the test must be repeated at least once, within 48 hours of the site becoming aware of the abnormal value.

For number 5, number 6, and number 7: after each IDMC review of similar AE, the committee will indicate the conditions under which it requires further notification and review of the subsequent similar AEs.

Note: the occurrence of a study pause in any other ongoing study with Ad26.COV2.S may trigger a study pause in further vaccination in the current study, if considered to be medically relevant. Any subsequent delayed study visits as a result of a delayed vaccination following a study pause are not considered to be protocol violations.

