To enable prompt response to a situation that could trigger pausing rules, the investigator should notify the sponsor's medical monitor or designee (AND fax or email the SAE form to Global Medical Safety Operations, if applicable), immediately and no later than 24 hours after becoming aware of any related AE of Grade 3 or above AND update the eCRF with relevant information on the same day the AE information is collected. A thorough analysis of all Grade 3 (or above) cases will be carried out by the sponsor's medical monitor or designee, irrespective of whether the criteria for pausing the study are met. Based on the pausing criteria, the sponsor's medical monitor or designee then decides whether a study pause is warranted. All sites will be notified immediately in case of a confirmed study pause. The sponsor's medical monitor or designee is responsible for the immediate notification of IDMC members and coordination of an IDMC meeting in case of a study pause no later than 24 hours after becoming aware.

Vaccinations for an individual participant may be suspended for safety concerns other than those described in the pausing criteria, at the discretion of the investigator if he/she feels the participant's safety may be threatened. The sponsor's medical monitor or designee may initiate IDMC review for any single event or combination of multiple events which, in their professional opinion, could jeopardize the safety of the participants or the reliability of the data.

Vaccinations for the study may be suspended for safety concerns other than those described above, or before pausing rules are met, if, in the judgement of the IDMC, participant safety may be threatened.

Resumption of vaccinations will start only upon receipt of written recommendations by the IDMC. The clinical site(s) will be allowed to resume activities upon receipt of a written notification from the sponsor. These recommendations from the IDMC will be communicated to investigators, IRB/IEC and relevant health authorities, according to local standards and regulations.

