10.4.3. Severity Criteria

Adolescents (12 to 17 Years of Age)

All AEs and laboratory data will be coded for severity using a modified version of the Food and Drug Administration (FDA) grading table, based on the version of September 2007 ([US DHHS FDA CBER 2007](#)), included in Section 10.5, Toxicity Grading Scale.

For AEs not identified in the grading table, the following guidelines will be applied:

Grade 1	Mild	Symptoms causing no or minimal interference with usual social and functional activities
Grade 2	Moderate	Symptoms causing greater than minimal interference with usual social and functional activities
Grade 3	Severe	Symptoms causing inability to perform usual social and functional activities and requires medical intervention
Grade 4	Potentially life-threatening	Symptoms causing inability to perform basic self-care functions OR medical or operative intervention indicated to prevent permanent impairment, persistent disability OR ER visit or hospitalization

The severity of solicited signs and symptoms will be graded in the reactogenicity diary by the participant based on the severity assessment provided in the reactogenicity diary and then verified by the investigator using the toxicity grading scale in Section 10.5. (Note: severity of the measured events will be derived from the diameter [for erythema and swelling] and the temperature measurements [for fever]).

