10.4.7. Contacting Sponsor Regarding Safety, Including Product Quality

The names (and corresponding telephone numbers) of the individuals who should be contacted regarding safety issues, PQC, or questions regarding the study are listed in the Contact Information page(s), which will be provided as a separate document.

10.5. Appendix 5: Toxicity Grading Scales in Adolescents (12 to 17 Years of Age)

Adapted from the FDA Guidance document “Toxicity Grading Scale for Healthy Adult and Adolescent Volunteers Enrolled in Preventive Vaccine Clinical Trials” (September 2007) (US DHHS FDA CBER 2007).

Tables for Clinical Abnormalities

Local Reaction to Injectable Product	Mild (Grade 1)	Moderate (Grade 2)	Severe (Grade 3)	Potentially Life Threatening (Grade 4)
Pain/Tenderness [#]	Aware of symptoms but easily tolerated; Does not interfere with activity; Discomfort only to touch	Notable symptoms; Requires modification in activity or use of medications; Discomfort with movement	Incapacitating symptoms; Inability to do work, school, or usual activities; Use of narcotic pain reliever	Hospitalization; Pain/tenderness causing inability to perform basic self-care function
Erythema [#]	25 – 50 mm	51 – 100 mm	>100 mm	Hospitalization; Necrosis or exfoliative dermatitis
Swelling [#]	25 – 50 mm	51 – 100 mm	>100 mm	Hospitalization; Necrosis

[#] Revised by the sponsor.

Vital Signs *	Mild (Grade 1)	Moderate (Grade 2)	Severe (Grade 3)	Potentially Life Threatening (Grade 4)
Fever (°C) ** (°F) **	38.0 – 38.4 100.4 – 101.1	38.5 – 38.9 101.2 – 102.0	39.0 – 40.0 102.1 – 104.0	> 40 > 104.0
Tachycardia – beats per minute	101 – 115	116 – 130	>130	Hospitalization for arrhythmia [#]
Bradycardia – beats per minute***	50 – 54	45 – 49	<45	Hospitalization for arrhythmia [#]
Hypertension (systolic) – mm Hg	141 – 150	151 – 155	>155	Hospitalization for malignant hypertension [#]
Hypertension (diastolic) – mm Hg	91 – 95	96 – 100	>100	Hospitalization for malignant hypertension [#]
Hypotension (systolic) – mm Hg	85 – 89	80 – 84	<80	Hospitalization for hypotensive shock [#]
Respiratory Rate – breaths per minute	17 – 20	21 – 25	>25	Intubation

* Participant should be at rest for all vital sign measurements.

** For oral temperature: no recent hot or cold beverages or smoking.

*** When resting heart rate is between 60 – 100 beats per minute. Use clinical judgement when characterizing bradycardia among some healthy participant populations, for example, conditioned athletes.

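### Protocol 10.4.3 points to Section 10.5 for laboratory grades that appear only in SAP 6.9, so a site could grade a laboratory AE lower than the SAP does when the pausing, notification and withholding rules are applied

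*Protocol*

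**What the plan says.** Protocol 10.4.3 covers laboratory results explicitly: "All AEs and laboratory data will be coded for severity using a modified version of the Food and Drug Administration (FDA) grading table". It cites the September 2007 FDA version and says the modified table is in Section 10.5. For anything outside that table it adds: "For AEs not identified in the grading table, the following guidelines will be applied". What follows is a four-step scale based on symptoms, function, and need for intervention or hospital care.

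Section 10.5 is introduced as "Tables for Clinical Abnormalities". It grades local reactions, vital signs, systemic symptoms and general illness.

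SAP 5.7.1.2 makes the same grading statement but refers to two SAP appendices, 6.8 and 6.9. SAP 6.8 reproduces the clinical scales. SAP 6.9 (Tables 10 to 12) holds the laboratory limits.

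Three parts of the protocol act on the grade during the study:

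- **Pausing rules (6.8).** Rule 2 includes one participant with a "persistent (upon repeat testing) Grade 4 laboratory abnormality that is determined to be related to study vaccine". Rule 6 applies when three participants in the same dose level, age group and regimen "experience a persistent (upon repeat testing) Grade 3 laboratory abnormality related to the same laboratory parameter" that is considered vaccine-related. The introduction to the rules limits these laboratory parts to testing done to investigate an AE.
- **Notification (6.8).** The site must inform the sponsor's medical monitor "immediately and no later than 24 hours after becoming aware of any related AE of Grade 3 or above".
- **Withholding (7.1).** A participant with a related Grade 4 event receives no further study vaccine.

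**The concern.** The protocol says it contains laboratory grades, and it does not. A site that records a low blood count as an AE and follows the protocol to the letter finds no row for it in Section 10.5. It then falls back on criteria that mostly ask how the participant feels and functions. Laboratory abnormalities can be severe without symptoms, so this scale can give a low grade to a value that the SAP treats as severe or potentially life-threatening.

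What is at stake is action at the time. A pause, a 24-hour notice or a withheld second dose has to be triggered when the value is seen. Regrading the same value later for the study report does not restore an action that was not taken.

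**Working it through.** No sample size or error rate is involved. The check is to set the two documents side by side and grade the same values under each.

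**Step 1: look for laboratory limits in the protocol.** Section 10.5 has four blocks: local reactions, vital signs, systemic symptoms and general illness. It has 0 laboratory rows. The last row is general illness, and Section 10.6 follows directly, so the gap does not look like lost text. Elsewhere, Appendix 2 lists tests without grades, and Appendix 8 lists typical MIS-C findings without grades.

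**Step 2: look for them in the SAP.** SAP 6.9 has serum, hematology and urine tables. Its hematology table has ten blood-count rows: absolute hemoglobin (2), hemoglobin change (2), WBC (2), lymphocytes, neutrophils, eosinophils and platelets. That leaves 10 − 1 = 9 that are not platelets.

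**Step 3: grade example values.** Assume that the participant has no symptoms, that no intervention or hospital care is needed, and that the value is outside local normal limits. Under the protocol fallback this fits Grade 1 (little or no effect on ordinary activity). The general-illness row in Section 10.5 gives the same grade.

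| Value (cells/mm³) | Protocol fallback, lowest reading | SAP 6.9 range | SAP grade | Difference |
|---|---|---|---|---|
| Neutrophils 400 | 1 | below 500 | 4 | 4 − 1 = 3 |
| Neutrophils 700 | 1 | 500–999 | 3 | 3 − 1 = 2 |
| Lymphocytes 400 | 1 | 250–499 | 3 | 3 − 1 = 2 |
| WBC 1,200 | 1 | 1,000–1,499 | 3 | 3 − 1 = 2 |

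**Step 4: follow the grade into the rules.** Suppose the neutrophil count of 400 is judged vaccine-related.

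- At Grade 4 it requires the 24-hour notice and meets the withholding criterion in 7.1. If it came from testing to investigate an AE and persists on repeat, it also meets pausing rule 2. The protocol requires that repeat within 48 hours of the site becoming aware of the abnormal value.
- At Grade 1 none of these applies.

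The other three values are Grade 3 in the SAP. They would require the notice when related, and they would count toward rule 6 if persistent and found during investigation of an AE. At Grade 1 they do neither.

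**Step 5: platelets.** Protocol 8.3.6.1 treats any count below 150,000/µL as suspected TTS, whatever its grade. The SAP's mildest platelet grade covers 125,000–140,000, so every graded platelet value is already below the cut-off. Rule 8 then pauses on "One or more cases of suspected TTS, possibly related to the vaccine". Platelets are therefore largely protected without a grade.

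**The case against.** The strongest reply is that this is a cross-reference slip with adequate cover elsewhere. Protocol 10.4.3 and 10.5 both name the FDA guidance, so a site could look the limits up. The study materials listed in Protocol Section 8 include a laboratory manual and eCRF completion guidelines, and either might carry grades. The fallback is worded for AEs, so a raw laboratory value that nobody records as an AE is not sent to it. The sponsor's medical monitor decides on pauses, the IDMC sees accumulated safety data, and for the higher grades "A thorough analysis of all Grade 3 (or above) cases will be carried out" whether or not a pausing criterion is met.

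Much of this stands. It makes a low grade possible rather than certain, and Grade 1 is the lowest reading. It does not remove the gap. The protocol says the modified table is in 10.5, and the listed site materials do not include the SAP. Part 1 had been running since 29 September 2021, while SAP version 1.0 is dated 11 February 2022. The sponsor's analysis of Grade 3 and higher cases depends on the grade, so an under-graded case does not reach it by that route.

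Three stronger readings are tempting, and the documents do not support them:

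- **Every scheduled blood count is affected.** Section 6.8 limits the laboratory parts of rules 2 and 6 to testing done to investigate an AE. A scheduled result reaches the notice or the withholding rule only if it is recorded as an AE. Counting scheduled draws therefore does not measure the problem.
- **The number of misgraded cases can be estimated.** The nearest figure, in Protocol 2.3.1, is vaccine-related neutropenia in 1.0% of adult Ad26 recipients against 0.5% on placebo. It covers any grade and adults only. Of the adults in that database, 84.2% received 5×10¹⁰ vp, which is 5 / 2.5 = 2 times this study's highest dose.
- **The reported laboratory results will be wrong.** SAP 5.7.2 grades laboratory abnormalities with SAP 6.8 and 6.9, so those tables are unaffected.

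**Conclusion.** The point holds and is minor. The protocol's reference to its own laboratory grades is wrong, and the fallback can put a laboratory AE two or three grades below the SAP. The exposure is confined to real-time use of the grade: the laboratory parts of rules 2 and 6 within their stated scope, the 24-hour notice, and withholding after a related Grade 4 event. It concerns mainly results other than platelets.

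This rests on three assumptions: that the site uses Section 10.5 and the fallback as written, that no unseen site document supplies the limits, and that the example values are outside local normal limits. How often a related Grade 3 or 4 laboratory abnormality would arise cannot be derived from the documents. It is more than an editorial slip because the rules that use the grade protect healthy adolescents during dosing, and later SAP grading cannot replace them.

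**What to change.** Copy the laboratory grades from SAP 6.9, at least the hematology table, into Protocol Section 10.5. Carry over the accompanying SAP rule that a value within local normal limits counts as normal, so that site and SAP grades are assigned on the same basis. The scope of the pausing rules need not change.

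The cost is one table and one sentence. The likely downside is a few more repeat tests within 48 hours, if more values are recognised as Grade 3 or 4.

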10.4.4. Special Reporting Situations

Safety events of interest on a sponsor study vaccine in an interventional study that may require expedited reporting or safety evaluation include, but are not limited to:

- Overdose of a sponsor study vaccine
- Suspected abuse/misuse of a sponsor study vaccine
- Accidental or occupational exposure to a sponsor study vaccine
- Medication error, intercepted medication error, or potential medication error involving a Johnson & Johnson medicinal product (with or without patient exposure to the Johnson & Johnson medicinal product, eg, product name confusion, product label confusion, intercepted prescribing or dispensing errors)
- Exposure to a sponsor study vaccine from breastfeeding

Special reporting situations should be recorded in the eCRF. Any special reporting situation that meets the criteria of an SAE should be recorded on the SAE page of the eCRF.

10.4.5. Procedures

All Adverse Events

All AEs, regardless of seriousness, severity, or presumed relationship to study vaccination, must be recorded using medical terminology in the source document and the eCRF. Whenever possible, diagnoses should be given when signs and symptoms are due to a common etiology (eg, cough, runny nose, sneezing, sore throat, and head congestion should be reported as “upper respiratory infection”). Investigators must record in the eCRF their opinion concerning the relationship of the AE to study therapy. All measures required for AE management must be recorded in the source document and reported according to sponsor instructions.

For all studies with an outpatient phase, including open-label studies, the participant must be provided with a “wallet (study) card” and instructed to carry this card with them for the duration of the study indicating the following:

- Study number
- Statement, in the local language(s), that the participant is participating in a clinical study
- Investigator’s name and 24-hour contact telephone number
- Local sponsor’s name and 24-hour contact telephone number (for medical personnel only)
- Site number
- Participant number
- Any other information that is required to do an emergency breaking of the blind

Serious Adverse Events

All SAEs that have not resolved by the end of the study, or that have not resolved upon the participant’s discontinuation from the study, must be followed until any of the following occurs:

- The event resolves
- The event stabilizes
- The event returns to baseline, if a baseline value/status is available
- The event can be attributed to agents other than the study vaccine or to factors unrelated to study conduct
- It becomes unlikely that any additional information can be obtained (participant or health care practitioner refusal to provide additional information, lost to follow-up after demonstration of due diligence with follow-up efforts)

Suspected transmission of an infectious agent by a medicinal product will be reported as an SAE.

Any event requiring hospitalization (or prolongation of hospitalization) that occurs during participation in the study must be reported as an SAE, except hospitalizations for the following:

- Hospitalizations not intended to treat an acute illness or AE (eg, social reasons such as pending placement in long-term care facility).
- Surgery or procedure planned before entry into the study (must be documented in the eCRF). Note: Hospitalizations that were planned before the signing of the ICF, and where the underlying condition for which the hospitalization was planned has not worsened, will not be considered SAEs. Any AE that results in a prolongation of the originally planned hospitalization is to be reported as a new SAE.

The cause of death of a participant in a study, whether or not the event is expected or associated with the study vaccine, is considered an SAE.

Information regarding SAEs will be transmitted to the sponsor using an SAE reporting form and safety report form of the eCRF, which must be completed and reviewed by a physician from the study site, and transmitted in a secure manner to the sponsor within 24 hours. The initial and follow-up reports of an SAE should be transmitted in a secure manner electronically or by facsimile (fax). Telephone reporting should be the exception and the reporter should be asked to complete the appropriate form(s) first.

Adverse Events of Special Interest

AESIs will be carefully monitored during the study by the sponsor. Suspected AESIs must be reported to the sponsor within 24 hours of awareness irrespective of seriousness (ie, serious and non-serious AEs) or causality assessment, following the procedure described above for SAEs and will require enhanced data collection.

